## Implementation framework: EPIS model.

The implementation approach is anchored in four stages of the EPIS conceptual model: Exploration, adoption/Preparation,

Implementation, and Sustainment. The strong evidence for SEEK's effectiveness has been underscored by its listing on the websites of the CDC, AHRQ, AAP, and by the California Clearinghouse for Evidence-Based Interventions in Child Welfare. Early adopters are increasingly implementing SEEK in primary care settings, including in Sweden. Four of the 5 healthcare systems in this proposal have implemented SEEK in some of their practices. However, practices within these systems operate independently of one another, and there should not be contamination among them. Each practice has its own lead physician, PCPs and administrative staff and several have integrated behavioral health. Given that early adopters are estimated to be 10% of those eligible and that medical innovations can take 17 years to be adopted, it is unlikely that SEEK's potential public health benefit will be realized without better methods for scaling up.

**Design.** The proposed implementation study is the first involving SEEK. We selected a rigorous Hybrid Type III design which is an approach to examine implementation outcomes while also examining SEEK's effectiveness in preventing CM, measured by EHR indicators. Type III designs are facilitated by good EHR systems due to the low cost of data routinely gathered for clinical, services, and financial purposes. This allows more resources to address the implementation outcomes of SEEK strategies in routine practice settings. In the past 4 years, over 80 papers reported use of hybrid designs. Practices will be randomized to one of the two training strategies (IND vs. MOC). Practices, however, will be able to select the facilitation strategy (SEEKonline or Traditional) as we are not able to require this of participants. The design accounts for heterogeneity in geography, size of healthcare systems, type of primary care (pediatric and family medicine), and presence of integrated behavioral health (see strong support letters from healthcare systems in Texas, Ohio, Utah, Wisconsin and North Carolina). As shown in Figure 2, professionals, office staff and parents are

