nested within practices which are nested within the 5 healthcare systems. The participating systems will be randomized to one of two start times - 9 or 16 months from project start date, beginning with one pediatric and one family medicine system (cohort 1). Staggering the start time addresses the capacity limitations of the training and research staff.

**Sample.** We will offer SEEK to the 5 healthcare systems. Inclusionary criteria are: 1) practices not already implementing SEEK, 2) practices providing primary care to children, and 3) agreement to participate. The systems have indicated a general commitment to this project; they include 59 practices with 306 PCPs. Our recruitment efforts in SEEK II were very successful with 75% (18/24) of practices agreeing to participate, including all the PCPs in those practices. We plan to study 13 pediatric and 35 family medicine practices. If more practices are interested, we will select the first 48 choosing to participate. In the unlikely event that fewer than 48 are interested, we will approach other healthcare systems. In addition to 5 system leaders, we will recruit 5 groups of participants: 1) all 48 practice leaders, 2) 275 PCPs, 3) 16 behavioral health professionals, 4) 96 ancillary staff, and 5) 288 parents (6 per practice). These estimates are based on current staffing. Smaller subsamples will be purposively selected for qualitative interviews according to practice type, training strategy and presence of integrated behavioral health.

We will also request limited consent from practice leaders and PCPs who opt out to briefly probe their decision. We will ascertain aggregated ICD-10CM-related diagnoses on all children 0-5 attending the practices (N~90,000). Based on our experience, we anticipate 60% of practice leaders and PCPs will be female as will be most of the other participants. Different regions provide diversity in terms of urban, suburban and rural locations, and racial/ethnic diversity (e.g., 2 systems serve a predominantly Latino population). Three systems have integrated behavioral health professionals. These contextual factors will be considered in all analyses.

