### **Timeline** (See Table 3 for timing of data collection)

Month 1-8: Hire and train project coordinator and research assistant. Randomly select first 2 healthcare systems (one pediatric, one family medicine). Recruit practices and randomly assign to SEEK training strategies; complete training. Practices select SEEKonline or Traditional strategy, SEEKonline connected to practices' EHRs, computerize study protocol, obtain IRB approvals

Month 5-48: Periodic webinars with PCPs and evaluation of participants, develop papers and presentations

Month 9: Begin implementing SEEK model in cohort 1 of healthcare systems and practices

Month 11-15: Repeat above process with cohort 2 of healthcare systems and practices

Month 16: Begin implementing SEEK model in cohort 2

Month 46-48: End of observation period, practices decide whether to continue using SEEK, final surveys

Month 49-60: Data will be obtained from practices' EHRs re. implementation (e.g., rate of screening, CM-related ICD-10 codes), final data analyses, prepare Final Report and papers

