### **Procedures**

**Pre-implementation Phase** (5 months). Recruitment will begin and we will identify a physician "champion" and an office staff member to lead implementation in each practice. Practices will choose by month 4 SEEKonline or the Traditional paper and pencil approach. To ease introduction of the SEEK model, we will address logistical issues such as for which checkups parents will complete the SEEK PQ and documentation in the EHR. SEEK Parent Handouts will be customized with information on local resources and PCPs will complete the SEEK Primary Care Provider Questionnaire (PCPQ) prior to the SEEK training.

**Implementation Phase.** In month 5, practices in cohort 1 will be randomized to one of the two SEEK training strategies (MOC or IND), stratified by practice type (pediatric or family medicine). At the end of training in month 8, PCPs will evaluate it. After the training, PCPs will be asked to participate in 3 webinars

every 4 months to discuss implementation and clinical issues. By month 8, interested practices will have SEEKonline connected to their EHR, ensuring interoperability. In month 9, the SEEK intervention will begin in cohort 1. Practice leaders, PCPs, behavioral health professionals and office staff will be asked to complete the online SEEK Adoption Survey, regardless of full participation. Parents also will begin completing surveys. Purposive subsamples from each group will be selected for 30-minute phone qualitative interviews. The process for cohort 2 will begin in month 11 and the SEEK intervention will start in month 16. Procedures are detailed under Human Subjects for addressing concerns of possible child abuse or neglect.

**Sustainment Phase.** Participants will be assessed at 12, 21 and 33 months post baseline regarding their thinking, feeling, behavior and experiences (see Table 3) to help inform understanding of SEEK's implementation and sustainment. At months 41 and 48, the observation period will end for cohorts 1 and 2. Final surveys and phone interviews will assess participants' thoughts and plans about continued use of SEEK. Following the grant period, practices that wish to continue utilizing the implementation strategies will be guided through the process of establishing real-world, not-grant funded contracting.

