**Aim 3. Examine the effectiveness of SEEK in reducing CM.** As in our previous studies, we will identify CM-related diagnoses, now via EHRs. We will review the EHR for each child (0-5) in each practice for two years prior to implementing SEEK and during implementation. The presence of CM-related ICD-10 codes will be recorded. The proportion of children with CM diagnoses before and during SEEK will be compared at each practice. Formal inference regarding the best estimate and statistical significance of pre-post differences will be based on a binary regression model with a random effect for site, similarly to Aim 1.

**Sample Size Considerations.** Our projected sample sizes (numbers of practices, professionals within each practice, and children in the practices) should provide good precision to estimate parameters and ample power to detect moderate associations. Table 4 below shows the detectable effect sizes for various comparisons, based on performing 2-sided .05-level tests and incorporate a 1.5-fold increase in variance and sample size to account for potential loss of power due to clustering of observations within practices and systems. In general, the detectable effect sizes are moderate, at plausible levels. We observed effect sizes of about 1.0 regarding Competence and Comfort in SEEK II. For Aim 2, assuming 90% of practices provide organizational information, we will estimate the rate of adoption of SEEK accurately,  $\pm$  15 percentage points.

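### MOC/IND randomisation is stratified by practice type only, so in cohort 2 chance can leave the arms unbalanced within a healthcare system; stratifying by system is a cheap improvement

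*Combined protocol and SAP*

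**What the plan says.** The unit of randomisation is the practice: the Design paragraph says "Practices will be randomized to one of the two training strategies (IND vs. MOC". Procedures, Implementation Phase, gives the only stratification factor: "practices in cohort 1 will be randomized to one of the two SEEK training strategies (MOC or IND), stratified by practice type". No allocation ratio, block size or second factor is stated.

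Participants are "nested within practices which are nested within the 5 healthcare systems". The systems start in two waves, "beginning with one pediatric and one family medicine system (cohort 1". That leaves 5 − 2 = 3 systems for cohort 2, for which the Timeline says only "Repeat above process with cohort 2 of healthcare systems and practices".

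On differences between systems, the Design paragraph states: "The design accounts for heterogeneity in geography, size of healthcare systems, type of primary care (pediatric and family medicine), and presence of integrated behavioral health". The Sample paragraph adds "Three systems have integrated behavioral health professionals", notes that two systems serve a mainly Latino population, and says that such contextual factors will be taken into account throughout the analysis.

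The Data Analysis Plan (General Considerations) puts random effects for system and practice in the models. The Aim 1 model for PCP Competence writes out a system term. The Aim 3 pre-post analysis uses a "binary regression model with a random effect for site, similarly to Aim 1". The Cost Analysis computes costs and cost-effectiveness ratios for each training arm and names no adjustment for system.

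**The concern.** Stratifying by type keeps the arms even among pediatric and among family medicine practices. It keeps them even within a system only where each stratum holds a single system. That is so in cohort 1 if each system is of one type. It cannot be so in cohort 2: three systems over two types put at least two systems in one stratum, and a system with both types would only add to the sharing.

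System matters because several features that could affect uptake vary between systems: state, patient population, EHR (four of the five use the same one) and integrated behavioral health (three of five). If one system's practices fall mostly in one arm, the MOC/IND contrast is partly a contrast between systems. At stake are some precision and the readability of the training comparison, chiefly for change in PCP scores and for the arm-level cost ratios.

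**Working it through.** **1. The plan's own figure.** The documents give no figure for balance by system. The nearest is Table 4, Aim 1a, PCPs: 137 per group, effect size 0.42, 80% power, two-sided 0.05, variance inflated 1.5-fold.

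d = (1.960 + 0.842) × √(2 / (137/1.5)) = 2.802 × √(2/91.33) = 0.415 (0.417 with the t distribution). This reproduces 0.42.

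**2. Assumptions.** From the documents: 48 practices (13 pediatric, 35 family medicine) in 5 systems, two of them in cohort 1. Practices per system are not given. I assume single-type systems, exact 1:1 allocation within a type stratum, and two cohort 2 systems in one stratum, with sizes varied.

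**3. Chance of an uneven split.** In a stratum of M practices with M/2 allocated to MOC, the number X of a system's m practices that go to MOC is hypergeometric(M, M/2, m).

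| Systems sharing a stratum | Event | Probability |
|---|---|---|
| 12 + 12 | 8:4 or worse | 0.220 |
| 12 + 12 | 9:3 or worse | 0.039 |
| 10 + 10 | 7:3 or worse | 0.179 |
| 8 + 8 | 6:2 or worse | 0.132 |
| 8 + 16 | smaller system 6:2 or worse | 0.193 |
| 4 + 20 | smaller system 3:1 or worse | 0.590 |
| 3 + 3 | each system wholly in one arm | 0.100 |

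For 12 + 12, for example: 2 × (1 + 144 + 4,356 + 48,400 + 245,025) / 2,704,156 = 0.220. With equal sizes the second system is the mirror image of the first. If allocation within the type stratum were not blocked, the figures would be larger: 0.388 for 12 practices, 0.344 for 10 and 0.289 for 8.

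**4. Information lost within a system.** Relative to an even split, the efficiency of a within-system comparison is 4X(m − X)/m². Its mean is 1 − (M − m)/(m(M − 1)), which for two equal systems (M = 2m) is 1 − 1/(2m − 1).

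- 12 + 12: 1 − 1/23 = 0.957
- 10 + 10: 1 − 1/19 = 0.947
- 8 + 8: 1 − 1/15 = 0.933
- 8 + 16, smaller system: 1 − 16/(8 × 23) = 0.91
- 4 + 20, smaller system: 1 − 20/(4 × 23) = 0.78

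**5. Information lost overall.** The other systems are already balanced under these assumptions, so the average loss over 48 practices is:

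- 24/48 × 4.3% = 2.2%
- 20/48 × 5.3% = 2.2%
- 16/48 × 6.7% = 2.2%

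The detectable effect moves from 0.415 to 0.415/√0.978 = 0.420, inside the rounding of Table 4.

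**6. What the model absorbs.** The Aim 1 mean is β0 + s + p + i + β1·POST + β2·POST·MOC, with s, p and i random intercepts for system, practice and PCP. The effect of interest, β2, is a difference in change. The system term shifts the level at both times equally and there is no system-by-POST term, so a system whose PCPs improve more for local reasons is not adjusted for.

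As an illustration, let that extra change be δ in one of two 12-practice systems, with splits of 8:4 and 4:8. Weighting practices equally, the arm difference in that stratum moves by δ × (8/12 − 4/12) = δ/3, or δ × 24/48 × 1/3 = δ/6 over all 48 practices. Averaged over randomisations the shift is zero.

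**The case against.** The strongest reply is that stratifying on one main factor and modelling the rest is an accepted choice, and that this plan does model system. That is right, and it removes several stronger readings that a reader might infer.

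- *That the Design statement on heterogeneity is contradicted.* It speaks of the design, not of the randomisation. The same paragraph goes on to the nesting in systems, and the analysis carries random effects for system and practice.
- *That the MOC/IND comparison is biased.* Imbalance under valid randomisation is chance. It neither biases the comparison in expectation nor inflates type I error.
- *That the Aim 3 pre-post model is unprotected because it names only site.* It refers back to Aim 1, whose model has a system term. It also compares before with during SEEK at each practice, so MOC/IND balance does not enter that contrast. Balance could matter only for the Aim 3 hypothesis comparing MOC with IND.
- *That the interview comparisons are unprotected.* They involve no hypothesis test, and respondents are chosen by role, practice type, training strategy and presence of behavioral health.

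It is also fair that the system sizes are assumed, that the stratification sentence names cohort 1 only (its use in cohort 2 is inferred from the Timeline), and that the overall loss with equal systems is small.

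Two gaps remain. The system term is an intercept on level while the effect is a change, and five systems give a weak variance estimate. For the cost ratios there is only the general statement about contextual factors, with no method attached.

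**Conclusion.** The point holds as a modest, inexpensive improvement, not as a flaw in validity. With practice type as the only stratifier, nothing in the randomisation balances MOC and IND within the cohort 2 systems that share a stratum.

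For equal systems of 8 to 12 practices, the chance of a split between 2:1 and 3:1 or worse is 13–22%. The average loss is 4–7% of the information in those systems, or about 2% overall, which leaves the 0.42 in Table 4 unchanged after rounding. Local imbalance is much larger when one system is small: 59% for 3:1 or worse with 4 + 20. The system random effect is only a partial remedy for outcomes measured as change.

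These sizes rest on single-type systems, exact 1:1 allocation within type, repetition of the cohort 1 method in cohort 2, and assumed practice counts per system.

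**What to change.** In Procedures, Implementation Phase, state for both cohorts that practices are randomised to MOC or IND stratified by healthcare system, and by practice type inside any system that has both, with blocked 1:1 allocation inside each stratum.

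This is one line in the randomisation specification, made before allocation. In the Timeline, recruitment comes before randomisation in each cohort, so the practices are known at that point. The 48 practices average 9.6 per system, so the strata are workable. If systems are single-type, stratification in cohort 1 does not change.

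The downside is up to one practice of imbalance per odd-sized stratum. With five single-type systems and 48 practices, at most four strata can be odd, because five odd numbers cannot sum to 48. The worst overall split is then 26:22, with efficiency 4 × 26 × 22/48² = 0.993.

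If the sponsor keeps type as the only stratifier, the plan should say that balance by system is left to the model, and add system and practice-type terms for change to the Aim 1 model.

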**Aim 1. Compare alternative approaches to implementation of SEEK with respect to clinical and implementation outcomes.** To address aim 1a, we will compare practices randomized to MOC to practices randomized to IND with respect to clinical and implementation outcomes. These include perceptions of the training from the PCPs' evaluations, scales from the SEEK PCPQ (e.g., Competence in addressing problems) and the PCP Survey (e.g., Ease of Delivery. We will also compare the groups with respect to rates of screening and parents' receipt of services and satisfaction with the PCP. For quantitative outcomes, statistical inference will be based on linear regression models; for binary outcomes, inference will be based on logistic regression models, accounting for repeated measures within PCP and system. For example, for PCPs reported Competence we will fit this model:  $E(\text{Competence}_{ijkl}) = \beta_0 + s_i + p_j + i_k + \beta_1(\text{POST}) + \beta_2(\text{POST})(\text{MOC-4})$  where Competenceijkl stands for the competence score measured at the lth time point (l=1 or 2 for baseline or follow-up respectively) of the kth PCP in the jth practice of the ith system, and  $s_i$ ,  $p_j$ ,  $i_k$  are random effects for system, practice and PCP respectively; POST=1 if it is a post-training measure and 0 otherwise, MOC = 1 if the PCP was trained using MOC and 0 if IND, and  $\beta$ 's are parameters to be estimated. Note this model assumes that the mean baseline scores are the same in both groups, as recommended for randomized studies. This model can be fitted using restricted maximum likelihood. To avoid possible biases due to selective attrition from the training, the primary analysis will follow the "intention to treat" principle including all those randomized. Secondary analyses will be based on groups defined by training received. To address Aim 1b we will compare practices who choose SEEK-online to practices who choose the traditional approach using the same statistical methods as described for Aim 1a. Outcomes of interest will include staff satisfaction, costs, rates of screening, receipt of services, and parental satisfaction.

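### Randomisation is stratified by practice type, but the written Aim 1a model has no practice-type term, so its standard errors may be slightly wider than needed

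*Combined protocol and SAP*

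**What the plan says.** The Design paragraph makes the practice the unit of allocation: "Practices will be randomized to one of the two training strategies (IND vs. MOC". The Implementation Phase paragraph under Procedures says that this is done "stratified by practice type (pediatric or family medicine", stated for cohort 1, with the process repeated for cohort 2. The strata are unequal: "We plan to study 13 pediatric and 35 family medicine practices".

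The Aim 1 paragraph of the Data Analysis Plan writes out one model, introduced by "For example, for PCPs reported Competence we will fit this model". Its fixed part is an intercept, POST and POST × MOC, with "POST=1 if it is a post-training measure and 0 otherwise, MOC = 1 if the PCP was trained using MOC and 0 if IND". The remaining terms "are random effects for system, practice and PCP respectively". On baseline it adds: "Note this model assumes that the mean baseline scores are the same in both groups". Practice type is in neither part of the model.

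The General Considerations paragraph adds only random effects and a test for sex differences. Practice type is analysed under Aim 2, not in the randomised Aim 1a comparison.

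**The concern.** When allocation is balanced within strata, differences between strata drop out of the true sampling error of the treatment contrast. A linear model that ignores the strata can leave those differences in the estimated error. The inference is then, if anything, conservative, and some precision on the main randomised comparison is given up.

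The random intercepts for system and practice can take up a constant difference in level between pediatric and family medicine practices. They do not vary over time, so they cannot represent a different pre-post change by practice type. Change is the quantity that Aim 1a targets; Table 4 frames the PCP comparison as changes in Comfort and Competence. A difference is plausible on the plan's own account: earlier SEEK studies were in pediatric practices only, and Aim 2 is built around variation between the two settings.

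There is also a prespecification issue. If the plan does not say whether the stratification factor enters the model, the choice between adjusted and unadjusted results stays open until the data are seen.

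**Working it through.** **1. The plan's own figure.** Inputs from Sample Size Considerations and Table 4: 137 PCPs per group, 80% power, two-sided 0.05, variance multiplied by 1.5.

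- Normal approximation: (1.960 + 0.842) × √(1.5 × 2/137) = 2.802 × 0.148 = 0.415.
- Noncentral t with 137/1.5 = 91.3 effective PCPs per group: 0.417, which rounds to the stated 0.42. Power at 0.42 is 0.81.

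The figure reproduces. It uses a flat inflation and takes no credit for stratification.

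**2. What the 1.5 factor implies.** With 275 PCPs in 48 practices (Sample), m = 275/48 = 5.73. ICC = 0.5/(5.73 − 1) = 0.106. Variance of a practice mean = 1.5/5.73 = 0.262 SD².

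**3. Repeated-measures PCP outcomes.** The documents give neither variance components nor a practice-type effect, so both are assumed. The components are system 0.02, practice 0.08, PCP 0.40 and residual 0.50, which give a cluster ICC of about 0.10, in line with step 2. The planned model was fitted by REML to 200 simulated trials per scenario, with 48 practices (13/35), 6 PCPs each and allocation stratified by type. It was compared with the same model plus practice type and practice type × POST. Entries are the planned SE divided by the SE with these terms; the first two columns are the assumed differences between practice types.

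| Level difference (SD) | Change difference (SD) | Each system one type | Types mixed within systems |
|---|---|---|---|
| 0 | 0 | 0.999 | 0.999 |
| 0.5 | 0 | 1.002 | 1.020 |
| 1.0 | 0 | 1.004 | 1.051 |
| 0 | 0.3 | 1.007 | 1.008 |
| 0.5 | 0.3 | 1.011 | 1.037 |
| 0 | 0.5 | 1.021 | 1.025 |

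A smaller run (12 trials, single-type systems) at a change difference of 0.25 SD gave about 0.3%. Both system layouts are shown because the Sample text labels the cohort 1 systems as one pediatric and one family medicine but does not say that every system is of one type.

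Rejection rates under the null were 3% to 7% with and without the added terms. The Monte Carlo error is √(0.05 × 0.95/200) = 1.5 percentage points, so no distortion of type I error was detectable.

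Applied to Table 4, the largest ratio gives 0.42/1.051 = 0.40. The adjusted detectable effect would lie between about 0.40 and 0.42.

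**4. Outcomes measured only after training.** Aim 1a also covers the training evaluation, the PCP Survey and parent satisfaction, and Table 3 marks no baseline for any of them. As an upper bound, suppose that the random effects absorb none of a type difference d. The between-type variance is (13/48)(35/48)d² = 0.197d², and the SE ratio is √[(0.262 + 0.197d²)/0.262]:

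- d = 0.25: √(0.274/0.262) = 1.02
- d = 0.5: √(0.311/0.262) = 1.09
- d = 1.0: √(0.459/0.262) = 1.32

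For parents (6 per practice, practice-mean variance 1.5/6 = 0.25), d = 0.5 also gives 1.09.

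**The case against.** The strongest reply is that the loss is hypothetical and small. If practice type is unrelated to the outcome, nothing is lost. A difference of 0.5 SD is large: its variance of 0.049 SD² would be 0.049/0.106, or about 47%, of all the between-practice variance implied by Table 4. The system and practice effects already take up most of a level difference. All of this stands, and it limits the size of the point.

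A reader might apply the practice-mean arithmetic to Competence itself: √[(0.262 − 0.049)/0.262] = 0.90, a gain of about 10%. The plan does not support that reading. Aim 1 specifies a repeated-measures model with three random effects and a common baseline mean, and for that model the same 0.5 SD difference in change gives 2% to 2.5%.

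It can also be said that the model is only an example, that the Design paragraph claims to account for type of primary care, and that the Sample paragraph promises that contextual factors will enter every analysis. But the written model is the template for Aim 1b and Aim 3. The Design statement concerns the design and names no model term. The factors listed just before the promise are location, ethnicity and behavioral health, not practice type. These passages make this a request to specify a term; they do not supply one.

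Finally, start time is assigned by system and there are only five systems, so a cohort main effect would use scarce system-level degrees of freedom. That stands, and the fix leaves it out.

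**Conclusion.** The mismatch is certain from the text: practice type stratifies the randomisation and is absent from the only Aim 1a model written out. Its cost is conditional on an effect that the documents do not give. For the repeated-measures PCP outcomes, assumed differences in change of 0.25 to 0.5 SD widen the SE by about 0% to 4%; the upper end also includes a 0.5 SD level difference with types mixed within systems. A level difference of 1.0 SD in mixed systems gives about 5%. For post-only outcomes the loss could reach about 9% at 0.5 SD if the system effect absorbs none of it.

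A reader might infer that the planned test is invalid, that the standard errors are certainly too wide, or that Table 4's 0.42 fails. None of these follows: no type I error distortion was detectable, the loss is zero without a type effect, and 0.42 reproduces without any credit for stratification. The sizes rest on assumed variance components and 200 trials per scenario. Binary outcomes were not simulated.

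**What to change.** State in the Aim 1 paragraph that practice type and practice type × POST enter the Aim 1a models as prespecified fixed effects, with practice type alone for outcomes measured only after training. Keep the random effects for system, practice and PCP. For the logistic models, add that the odds ratio, already conditional on the random effects, is also conditional on practice type.

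Cohort × POST may be listed as a secondary term. A cohort main effect is not needed, because cohort is assigned at system level.

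The cost is one sentence in the plan and one or two practice-level degrees of freedom, with no new data. In the simulation with no type effect, the added terms raised the SE by about 0.1%.
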